### **Study Visit 1 (screening)**

Once the participants arrive, the study will be explained in full detail. If the participant agrees, he/she will be consented into the study and the participant will be given a copy of the informed consent.

Once consent is obtained, and eligibility is confirmed, the following study related procedures will be conducted:

- Demographics: sex, age, ethnicity, and race will be collected
- Anthropometric Measurements: height, weight, neck circumference will be collected.
- Current Medications: all current medications will be collected.
- Medical History Assessment: information will be collected regarding historical spirometry data, PaCO2 level at the time of NIV initiation, COPD history questionnaire, smoking history and other relevant medical history including the diagnosis of Sleep disordered breathing.
- Physical examination with vital signs to include HR, BP, RR, and SPO2 maintained at least 88%, and chest auscultation.
- Administration of CAT and STOP-BANG questionnaires.
- Urine pregnancy test for women of childbearing potential
- Mask Fitting: Participants may have up to two mask fittings in order to determine the best possible provided mask while using the Vector NIV device.

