## EFL Screening/Determination and EPAP Titration

- For the EFL Screening/Determination and EPAP Titration procedure, the following device settings will be applied:

• Pressure Support	6 cmH 2 O
• Max Pressure	26 cmH 2 O
• EPAP Min / EPAP Max	4 / 20 cmH 2 O
• EPAP setting	Auto
- EFL Determination: The participant will be asked to lie supine or semi-recumbently while breathing into the Vector NIV device using the selected mask initially for 5 minutes. This device has a screening test that has the capability of detecting and estimating the severity of EFL. If it is determined that the participant does not have EFL after 5 minutes by the device screening indicator, the participant will not continue in the study. After the screening is complete, participants will be asked a couple of questions about their experience.
- EPAP Titration: If it is determined by the Vector NIV device that the participant has EFL, the Vector NIV device will be changed from screening mode to therapy mode to delivery BiPAP therapy. The participants will then breathe on the Vector NIV device in the supine position for an additional 20 minutes approximately. During the additional 20 minutes of breathing, the device will automatically increase the EPAP (and concurrently and proportionally the IPAP) until the EFL is abolished (falls below the predetermined EFL threshold). After the titration is complete, participants will be asked a few questions about their experience
- While the automatic EPAP Titration is being performed all participants' SpO2 will be monitored via finger pulse oximetry. Oxygen will be provided to patients at the clinician's discretion.
- Patient must stay awake during the EPAP Titration. If the patient falls asleep, they will be awoken by study staff.
- The Final EPAP that is determined to abolish the participants EFL will be recorded. If the determined EPAP pressure is 6cmH2O or higher, the participant may continue to study visit 2. If the determined EPAP is below 6cmH2O then the participant will not be scheduled for study visit 2.
- Participants that are determined to have EFL and a titrated EPAP  $\geq$  6cmH2O will be eligible to continue in the study.

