### **VI. Selection and Withdrawal of Subjects:**

#### **Inclusion Criteria**

1. Age  $\geq$  40 years of age;  $\leq$  80 years of age
2. Ability to provide consent
3. COPD patients with hypercapnia (as defined as  $\geq$  52mmHg) who are either current NIV users or naïve to NIV
4. On average, use NIV more than 4 hours per night (Current NIV users).
5. Must present with EFL via screening of the Vector device at 3 cmH2O
6. Have an EPAP to abolish EFL greater or equal to 6cmH2O

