#### **Exclusion Criteria:**

1. Any major non-COPD uncontrolled disease or condition, such as congestive heart failure, malignancy, liver or renal insufficiency (that requires current evaluation for liver or renal transplantation or dialysis), amyotrophic lateral sclerosis, or severe stroke, or other condition as deemed appropriate by investigator as determined by review of medical history and / or participant reported medical history
2. Suffering from a COPD exacerbation (Defined as hospital admission, ER/urgent care visit, MD visit with medication change or other intervention deemed to be

clinically significant by the investigator at the time of data collection or in the 14 days prior to data collection

3. Self-reported Pregnancy or positive pregnancy test for women of childbearing potential.
4. Employee or family member that is affiliated with Philips
5. Currently employed by a manufacturer of respiratory products or family member employed by a manufacturer of respiratory products
6. Any history of giant bulla (size >1/3 hemi-thorax)
7. History of pneumothorax ≤ 6 months
8. Participants currently using a PAP or NIV device at home with a documented EPAP setting on their current device that is greater than the calculated EPAP determined during the therapy session of the screening visit (Current NIV Users).
9. Life expectancy ≤12 months as determined by clinical investigator
10. Low BP: Systolic <90
11. Recent cranial surgery (i.e, less than 1 year)
12. Impaired swallowing as reported by participant or diagnostic exam
13. Recent upper airway or GI surgery within the past 6 months
14. Unable to be fitted with mask
15. Excessive secretions as reported by clinical investigator/physician assessment, inability to maintain a patent airway or adequately clear secretions, or at risk for aspiration of gastric contents
16. Diagnosed with acute sinusitis or otitis media
17. Epistaxis, causing pulmonary aspiration of blood
18. Existing respiratory failure
19. Participants who are naïve to NIV (Cohort 2) that use the device fewer than 3 out of 7 nights during the second week of the 2-week acclimation period
20. Participants who are naïve to NIV (Cohort 2) that average less than 4 hours of device use during the second week of the 2-week acclimation period

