### ***B. Contraindications:***

- Inability to maintain a patent airway or adequately clear secretions
- At risk for aspiration of gastric contents
- Diagnosed with acute sinusitis or otitis media
- Epistaxis, causing pulmonary aspiration of blood
- Hypotension, defined as systolic BP < 90
- Existing respiratory failure

There will be no restrictions on concomitant medications during the course of the study. If medications change during the study, participants will be asked to let their pulmonologist know.

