## **XVIII. Risk and Benefit Analysis**

### **A. Potential Risks and Discomforts**

Adverse effects of NPPV are usually minor and manageable. The masks may cause some discomfort and air pressure and flow have adverse effects. All adverse effects encountered, including mask discomfort, nasal or mouth congestion or dryness, eye irritation, gastric insufflation, and nasal bridge ulceration will be recorded on data sheets that are part of the case report form.

The risks of using the Vector NIV Device are minimal. Use with the NPPV devices may cause a decrease in the inability to adequately clear secretions, an increased risk for aspiration of gastric contents, increase in symptoms of sinusitis or otitis media, and decrease in blood pressure. These are minimal risks of using the device and should they occur during the course of the study, they be recorded. Other more serious adverse effects, such as pneumothorax or aspiration pneumonia, are distinctly unusual

in the outpatient setting, but will be recorded if they occur. Significant adverse events will be reported to the Institutional Review Board. Patients currently on NIV may find Vector to be less comfortable than their previous NIV, but this is not a real medical risk.

Arterial blood gas determinations are part and parcel of routine pulmonary function testing and are performed by trained respiratory therapists on a daily basis. The blood gas draws as part of this study is consistent with usual care in initiating NIV. The research technician will employ the usual precautions while performing such a procedure by employing adequate aseptic technique. The arterial blood gas sampling test can cause pain, tenderness or swelling at the puncture site and possibly bleeding, local infection, lightheadedness or fainting.

Standard PSG (sleep study) risks might include: complaints of skin irritation from the adhesives or tapes used to secure the electrodes and any necessary skin preparation.

Participants may also find some of the chemical adhesive smells offensive. The participant may sleep poorly.

The patient may sleep poorly during the nocturnal sleep study and thus may be sleepy the next day. If the patient is too sleepy to drive home, other forms of transportation will be utilized.

COVID-19 is a risk with any in-person activity, but proper mitigation strategies, including COVID-19 screening, disinfection, and other site safety procedures, will be implemented to minimize patient risk.

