## Appendices

### Appendix A

#### VECTOR TITRATION PROTOCOL

Device titration will take approximately 3 hours. There will be 2 separate Titration periods. The Vector Auto EPAP will be titrated in both fixed pressure and using AVAPS that will auto titrate Pressure Support based up on a set tidal volume. Each titration session will last approximately 1.5 hours. Prior to the initiation of the device titration, a baseline TCO2, SPO2, Respiratory Rate will be recorded. If existing NIV user, the device titration initial pressure setting will start at their current device pressure settings.

Immediately prior to conducting the Vector Titration, a resting awake tidal volume determination will be conducted. The participant will be asked to sit in a chair for 30 minutes with the mask, awake, and quietly breathing. Participants will breathe on the device that is manually pressure titrated to the starting tidal volume calculation using 8 ml/kg of ideal body weight (Table 1). After 5 minutes of breathing on the device with the stable target tidal volume, a Borg Scale will be used to assess the patient's level of breathing comfort. This evaluation will continue until the participant's pressure support is manually titrated to the stable target tidal volume that is equivalent to 9 ml/kg and 10 ml/kg of the participant's ideal body weight. The setting that provided the most optimal Borg Scale rating will be the setting used for the study. If optimal tidal volume cannot be achieved after 10 minutes at 10ml/kg of ideal body weight, the participant will be then transitioned to the AVAPS titration protocol.

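### The readable text schedules no blood pressure reading after the Visit 1 examination and none on the device, although systolic BP below 90 is a contraindication and a fall in BP is a named risk

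*Combined protocol and SAP*

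**What the plan says.** The protocol refers to BP in four places.

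- **Entry.** Exclusion criterion 10 reads "Low BP: Systolic <90".
- **Device use.** Section VII.B lists as a contraindication "Hypotension, defined as systolic BP < 90".
- **Risk.** Section XVIII.A says these devices may cause, among other effects, "increase in symptoms of sinusitis or otitis media, and decrease in blood pressure". It calls the risks minimal and says they will be recorded if they occur.
- **Measurement.** Study Visit 1 (screening) includes "Physical examination with vital signs to include HR, BP, RR" and SpO2. This is the only scheduled BP in the readable text.

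Two places describe what is measured around titration. In the Visit 1 EPAP titration, SpO2 "will be monitored via finger pulse oximetry". For the Visit 2 titration, Appendix A says "Prior to the initiation of the device titration, a baseline TCO2, SPO2, Respiratory Rate will be recorded". It describes two titration periods: "Each titration session will last approximately 1.5 hours".

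The Withdrawal part of Section VI lets the investigator discontinue a participant for, among other things, changes in vital signs.

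**The concern.** The protocol states a BP limit for using the device and a risk that could push a participant below it, but after Visit 1 it schedules no reading that would show whether this has happened. Three of its own provisions depend on such a reading.

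1. The contraindication bears on continued use as well as entry, but it is not rechecked.
2. A fall in BP is to be recorded if it occurs. Without a measurement, a symptomless fall cannot be recorded. If the adverse event listings show no hypotension, that would partly reflect the absence of readings.
3. Discontinuation for changes in vital signs needs later vital signs to act on.

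The point matters most for the NIV-naïve cohort. They first meet positive pressure after the Visit 1 examination and use the device at home for two weeks. At Visit 2 they are rechecked for usage and 90% EPAP, but not for BP. Current users already tolerate NIV, so for them the Vector settings are the new element. The protocol also puts no restriction on concomitant medication (end of Section VII.B), so a Visit 1 value may not represent BP later on.

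**Working it through.** The plan gives no figure to reproduce. The check is a count of scheduled BP readings, stage by stage.

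| Stage (section) | Listed measurements | BP listed? |
|---|---|---|
| Visit 1 physical examination (Study Visit 1) | HR, BP, RR, SpO2, auscultation | Yes, 1 |
| Visit 1 EPAP titration | SpO2 | No |
| Visit 1 standard-of-care titration, naïve cohort (NIV SOC Titration) | None stated in that section | No |
| Visit 2 (Randomization and Titration) | Questionnaires, activity monitor, device data for the naïve cohort | No |
| Visit 2 titration (Appendix A) | TCO2, SpO2 and respiratory rate at baseline; Borg rating | No |
| Home periods (Phone Follow-ups) | Calls about problems and compliance | No |
| Visits 3 and 4, overnight (PSG montage) | Belts, position, ECG, EEG/EOG/EMG, oximetry, microphone, leg leads, transcutaneous CO2 | No |
| Visits 3 and 4, morning (Arterial Blood Gas) | ABG and SpO2 on room air after seated rest | No |

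**Result:** 1 scheduled reading at Visit 1, listed before any study pressure is applied, and 0 at Visits 2, 3 and 4. The number listed while a participant is on the device is 0.

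The schedule-of-events table agrees: it marks history and physical once and has no vital-signs row. It came through broken, without a Visit 4 column in its header, so it adds little to the section text.

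**Where readings could be taken.** The Visit 2 titration lasts 2 × 1.5 h = 3 h, and staff already record vital measures at its start. Visits 3 and 4 each include an attended night in the sleep laboratory on therapy. No new visit is needed.

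**Number of readings.**
- Visit 2: 1 baseline + 2 (end of each titration period) = 3.
- Visits 3 and 4: 1 + 1 = 2.
- Current users: 3 + 2 = 5.
- Naïve cohort: add a baseline and an end-of-period reading at the Visit 1 standard-of-care titration. That is 2 readings if it has one period and 3 if it follows the two-period layout of Appendix A, giving 5 + 2 = 7 or 5 + 3 = 8.
- The cohort split is not stated. For 30 completers the total lies between 30 × 5 = 150 (all current users) and 30 × 8 = 240 (all naïve).
- If all 50 who may be enrolled went through every visit, the range is 50 × 5 = 250 to 50 × 8 = 400.

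**The case against.** The strongest case against has four parts.

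**Other safeguards exist.** Titration is started under the supervision of the investigator, coordinator or another health professional. Adverse events are collected throughout, and unscheduled visits are allowed. A reader might infer that any fall below 90 would go undetected. The documents do not support that: a symptomatic fall may well be reported, and an unscheduled or routine-care reading could reveal a silent one. What stands is that no scheduled procedure in the readable text would find a symptomless fall.

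**The text is incomplete.** The settings under the Vector titration headings in Appendix A are missing, and part of Appendix B is redacted. The Randomization section also points naïve participants in the standard-of-care arm to established site titration protocols that are not reproduced. Any of these could include BP. This limits the claim but does not answer it, since the readable Appendix A names its baseline measures and BP is not among them.

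**The limit is an entry limit.** A reader might take systolic below 90 as an on-treatment stopping rule that the plan fails to apply. It is not written as one. It is an exclusion and a contraindication, and other contraindications, such as sinusitis or epistaxis, also have no scheduled recheck. BP differs because Section XVIII.A names its fall as a device effect, it can be silent, and a cuff settles it in a minute.

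**The risk is called minimal, and current users already tolerate NIV.** That is fair and lowers the priority. A reader might also infer that Vector lowers BP more than standard NIV because it raises EPAP and IPAP together. The documents give no evidence for this, and no incidence from which to estimate expected cases.

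One further overreading concerns home use. Time on the device is 28 to 42 days of Vector for a current user. For a naïve participant it is 14 + 2 × 28 = 70 to 16 + 2 × 42 = 100 days. These days should not be read as exposure that added clinic readings would cover. Overnight BP at home would remain unmeasured.

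**Conclusion.** The gap is real but modest. In the readable text there is one scheduled BP reading, at Visit 1, and none afterwards or on the device, despite a stated limit of systolic 90 and a named risk of a fall.

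The conclusion assumes that the missing settings, the redacted part of Appendix B and the unseen site titration protocols contain no BP check. If they do, the point reduces to citing it in the protocol and adding a response rule. It assumes nothing about how often BP falls, or about any difference between Vector and standard NIV.

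The primary endpoint, daytime PaCO2, is not called into question. This is a cheap safety improvement of low to moderate priority.

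**What to change.** 1. **Titration (Appendix A).** Add BP to the TCO2, SpO2 and respiratory rate baseline, and repeat it on the device at the end of each titration period. Apply the same to the naïve cohort's standard-of-care titration at Visit 1. For that cohort, take the Visit 2 baseline reading before randomisation, so that a low value after acclimation is seen before a treatment order is assigned.
2. **Visits 3 and 4, when attended on site.** Take one reading on the device in the sleep laboratory, before lights-out or at waking. A seated reading during the rest before the ABG is optional. If taken, state that it checks resting BP off the device only, because it would miss a fall that occurs only under pressure.
3. **Response (Section VI, Withdrawal).** State that a systolic BP below 90 confirmed on repeat requires same-day investigator review and a documented decision to continue, adjust pressures, hold or withdraw, including how ventilation is provided meanwhile. Do not make a hold automatic: these participants are hypercapnic and may depend on the therapy.

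**Cost.** Five cuff readings per current user and seven or eight per naïve participant, at existing visits, plus an occasional confirmatory or optional reading. The Visit 3 and 4 readings are lost if those visits are done remotely. The main downside is occasional loss of a within-participant comparison when therapy is changed after a low reading. The enrolment effect of a low pre-randomisation value in the naïve cohort cannot be estimated from the documents.

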##### Vector Device Settings Fixed Pressure Titration:

##### Vector Device Setting – AVAPS

Once the auto EPAP has settled (approximately 20 minutes), if SpO2 remains low, tidal volume adjustments can be made (up to 10ml/kg IBW) based on the physician's discretion.

**Table 1. AVAPS Tidal Volume Setting \* Based on 8ml/kg**

Height	Male	Female
5'0"	400	360
5'1"	420	380
5'2"	440	400
5'3"	460	420
5'4"	470	440
5'5"	490	460
5'6"	510	470
5'7"	530	490
5'8"	550	510
5'9"	570	530
5'10"	580	550
5'11"	600	570
6'0"	620	580
6'1"	640	600
6'2"	660	620
6'3"	680	640
6'4"	690	660
6'5"	710	680
6'6"	730	700

## Appendix B

### BiPAP/CPAP/Mask fitting Protocol

#### POLICY

Temple hospital sleep therapy to follow the BiPAP/CPAP/Mask fitting protocol, shall determine BiPAP/CPAP settings based upon each patient's diagnosis and immediate clinical demand.

#### PURPOSE

The objective is to facilitate the emergent application, management, and timely discontinuation of BiPAP/CPAP therapies via facemask.

#### SCOPE

The following guidelines transcend the solely physician driven approach to BiBAP/CPAP therapies for acute hypercapnic respiratory failure, thereby allowing the SCP to make timely, necessary adjustments to manage the patient's immediate clinical demand as his/her condition changes.

#### SETTINGS

When treating acute hypercapnic respiratory failure, the distance between the IPAP and EPAP pressures is of primary importance. Ventilatory assistance increases as the distance between these two settings widens. For example, an IPAP/EPAP of 16/6 provides greater ventilatory assistance than does 12/6, whereas both settings provide the same degree of oxygenation augmentation, because both 16/6 and 12/6 have EPAP settings of 6 cm H2O.

All settings are considered dynamic, in that they may need adjustment to meet patient demand as his/her condition changes. The following guidelines provide a standardized basis from which to initiate settings and make said changes.

#### BiPAP settings for Acute Hypercapnia

1. [REDACTED]

2.

3.
